3.1.1 Administrative structure of the trial

The trial is sponsored by AbbVie in the US and Boehringer Ingelheim (BI) ex-US.

The trial is planned to be conducted at sites participating in the 1311.2 trial, i.e. it will be conducted at approximately 24 sites in 4 different countries.

Boehringer Ingelheim has appointed a Trial Clinical Monitor (TCM), responsible for coordinating the activities required in order to manage the trial in accordance with applicable regulations and internal standard operating procedures (SOPs), directing the clinical trial team in the preparation, conduct and reporting of the trial and ensuring appropriate training and information for Local Clinical Monitors (CML), Clinical Research Associates (CRAs) and investigators of participating countries.

Data management will be done by BI according to BI SOPs and the Statistical Evaluation will be done by AbbVie according to their SOPs. For these activities a Trial Data Manager and a Trial Statistician have been appointed. A list of responsible persons will be available in the Trial Master File (TMF).

The organisation of the trial in the participating countries will be performed by the respective local BI-organisation (Operation Unit (OPU)) or by a Contract Research Organisation (CRO) with which the responsibilities and tasks have been agreed and a written contract filed before initiation of the clinical trial. In each OPU participating in this study, a CML will be appointed responsible for coordinating the activities required, in order to manage the trial in accordance with applicable regulations and internal SOPs in the countries covered by the respective BI OPU.

Proprietary confidential information.

© 2018 Boehringer Ingelheim International GmbH or one or more of its affiliated companies. All rights reserved.

This document may not - in full or in part - be passed on, reproduced, published or otherwise used without prior written permission.

A Co-ordinating Investigator has been nominated to coordinate investigators at different sites participating in this multicentre, multinational trial. Tasks and responsibilities for the Coordinating Investigator will be defined in a written contract filed before initiation of the trial.

Details of the trial supplies including responsible institutions are given in [Section 4](#) of this protocol.

The Investigator Site File (ISF) will be maintained at the sites as required by local regulation and BI-SOPs. A copy of the essential ISF documents will also be kept as an electronic TMF document according to BI SOPs.

A central laboratory service and an Interactive Response Technology (IRT) vendor will be used in this trial. Details will be provided in IRT Manual and Central Laboratory Manual, available in ISF.

Safety will be monitored by an independent Data Monitoring Committee (DMC).

3.1.2 Data Monitoring Committee (DMC)

The trial will include the review of data by an external, independent DMC, including an independent statistician. The purpose of the DMC is to ensure the welfare of subjects participating in this trial is maintained by monitoring the trial for possible, untoward harmful effects or inappropriate frequency of adverse events for this class of medication. The DMC will evaluate and analyse accrued, unblinded safety and efficacy data in order to recommend whether the trial should continue, be modified or stopped due to safety or lack of efficacy concerns. For details regarding DMC structure and scheduled meetings, please consult the DMC charter.

Sponsor will agree with the DMC a set of strictly defined stopping criteria for the study level, to be included into the DMC Charter.

The final DMC Charter will be available before study initiation.

3.2 DISCUSSION OF TRIAL DESIGN, INCLUDING THE CHOICE OF CONTROL GROUP(S)

Study 1311.13 is designed as an open label extension clinical trial, and is expected to generate additional safety information to support the registration submission. As noted in [section 4.1.3](#) below, the intermediate dose (90 mg) from the 1311.2 study will be used, with the option of moving to a higher dose (180 mg) if inadequate clinical activity is noted. Our goal in this study is to obtain safety and efficacy data following long-term drug administration. As an open-label study, we realize that no powered or controlled analysis can be obtained. However, we will be able to evaluate initial tendencies and at the same time permit our early study participants an opportunity to maintain access to a therapy that initially has shown the potential to have significant clinical benefit.

3.3 SELECTION OF TRIAL POPULATION

Eligible patients from trial 1311.2 will be offered participation in this OLE trial. The check for patient eligibility will be based upon a successful completion (cf. [Section 3.3.2](#)) of the previous trial and on signing the Informed Consent for the OLE.

A 40 % dropout rate from preceding trial is expected, leaving approximately 100 patients to be entered in this trial.

A log of all patients included into the study (i.e. having given informed consent) will be maintained in the ISF at the investigational site.

3.3.1 Main diagnosis for study entry

Moderate to severe chronic plaque psoriasis.

3.3.2 Inclusion criteria

1. Patients with moderate to severe chronic plaque psoriasis, who have successfully completed the preceding trial, 1311.2. Successful completion of preceding trial is defined as either of the following:
 - a. Completion of the entire follow up period, thus reaching End-of-study (EOS) visit.
 - b. Loss of response, defined as decrease in response to <PASI₅₀ at any time from week 24.
2. Patient must give informed consent and sign an approved consent form prior to any study procedures in accordance with Good Clinical Practice (GCP) and local legislation
3. Applicable only for female patients:

Negative urine pregnancy dip stick test at the roll-over visit, and if available at roll-over visit, negative

Serum β-Human Chorionic Gonadotropin (β-HCG) test ([cf. Section 3.3.4.1](#)).

In addition:

Women of childbearing potential (not surgically sterilized and between menarche and 1 year postmenopausal), that, if sexually active agree to use one of the appropriate medically accepted methods of birth control in addition to the consistent and correct use of a condom from date of the roll-over visit until 12 weeks after last treatment in this trial. Medically accepted methods of contraception's are: ethinyl estradiol containing contraceptives, diaphragm with spermicide substance, and intra-uterine-device.

OR

Proprietary confidential information.

© 2018 Boehringer Ingelheim International GmbH or one or more of its affiliated companies. All rights reserved.

This document may not - in full or in part - be passed on, reproduced, published or otherwise used without prior written permission.

Female patients which have vasectomized sexual partner(s) (vasectomy at least 1 year prior to enrolment).

OR

Surgically sterilized female patients with documentation of prior hysterectomy, tubal ligation or complete bilateral oophorectomy.

OR

Postmenopausal women with postmenopausal is defined as permanent cessation ≥ 1 year of previously occurring menses.

3.3.3 Exclusion criteria

1. Patients who experienced any drug related Serious Adverse Event in the preceding trial
2. Patients who have developed guttate, erythrodermic or pustular psoriasis or drug-induced psoriasis (as diagnosed by the investigator), during the preceding trial 1311.2.
3. Evidence of current or previous clinically significant disease, medical condition other than psoriasis, or finding of the medical examination (including vital signs and (electrocardiography (ECG)), that in the opinion of the investigator, would compromise the safety of the patient or the quality of the data.
4. Known clinically important acute or chronic infections including hepatitis, HIV. In regards to Tuberculosis the following applies:
 - Signs or symptoms suggestive of current active or latent tuberculosis upon medical history, physical examination and/or a chest radiograph (both posterior-anterior and lateral views, taken within 3 months prior to the first administration of study drug and read by a qualified radiologist).
 - History of latent or active TB prior to screening, except for patients with documented completion of an adequate treatment regimen, at least 6 months prior to the first administration of study agent.
 - Positive QuantiFERON-TB Gold In-Tube test (IGRA) within 2 months prior to the roll-over visit (if available) (cf. [Section 3.3.4.1](#)), in which active tuberculosis has not been ruled out. This does not apply to patients with history of latent tuberculosis with documented completion of an adequate treatment regimen, at least 6 months prior to the first administration of study agent.
5. Patients who have developed malignancy, or suspicion of active malignant disease during the preceding trial 1311.2 (except treated cutaneous squamous cell or basal cell carcinoma or carcinoma in situ of the cervix that have been adequately treated).

6. Intake of restricted medications (cf. [Section 4.2.2.1](#)) or other drugs considered likely to interfere with the safe conduct of the study, as assessed by the investigator.
7. Alcohol or drug abuse within 3 months prior to the roll-over visit that would interfere with trial participation or any ongoing condition leading to a decreased compliance to study procedures in the opinion of the investigator.
8. Any clinically significant laboratory abnormalities based on the last available lab results received during the preceding trial (according to the investigator's medical assessment) (cf. [Section 6.2.2.1](#)).
9. Pre-menopausal woman who is pregnant or nursing

Note:

As there might be other medical and social issues, not covered by the above criteria it is left to the discretion of the investigator to exclude patients based on clinical judgment, even if other eligibility criteria are satisfied.

3.3.4 Removal of patients from therapy or assessments

3.3.4.1 Removal of individual patients

An individual patient is to be withdrawn from the trial if:

- The patient withdraws consent, without the need to justify the decision.
- Clinically important acute or chronic infections including hepatitis, HIV and tuberculosis (including latent tuberculosis), or a positive interferon gamma release assay (IGRA) testing for tuberculosis (cf. [Table 5.2.3: 1](#)) according to test at the roll-over visit.
- The patient is no longer able to participate for other medical reasons (e.g. pregnancy, surgery, AEs or other diseases).

A patient can be withdrawn after discussion between sponsor and investigator if eligibility criteria are being violated or if the patient fails to comply with the protocol (e.g. non-attendance at study assessments). Note: Patients using restricted medications (cf. [Section 4.2.2](#)), will continue to be followed up to collect safety data but their efficacy and PD endpoints assessed after administration of restricted medications will not be considered for analysis.

If a patient withdraws from the study after informed consent, this will be documented and the reason for withdrawal will be recorded in the case report form (CRF). This data will be included in the trial database and will be reported. At the time of discontinuation a complete end of treatment (Extended EOT) evaluation should be performed according to [Flow Chart](#) and the patient will subsequently enter a follow up period of 12 weeks, until a final Extended EOS visit is performed. If the decision to discontinue study participation is taken in between study visits in the treatment period, an Extended EOT visit is to be scheduled at the earliest convenience and by the latest at the next upcoming visit according to [Flow Chart](#) and the information will be recorded in the CRFs.

Proprietary confidential information.

© 2018 Boehringer Ingelheim International GmbH or one or more of its affiliated companies. All rights reserved.

This document may not - in full or in part - be passed on, reproduced, published or otherwise used without prior written permission.

If the decision to discontinue is taken in the 12 week follow up period, an early Extended EOS visit is to be scheduled at the earliest convenience. The procedures described at Extended EOS will be performed and the information will be recorded in the CRFs. The withdrawals will be discussed in the final report of the study.

If a patient becomes pregnant during the trial, the investigational product needs to be stopped. The patient will be followed up until birth or otherwise termination of the pregnancy. The data of the patient will be collected and reported in the clinical trial report until last patient last visit and any events thereafter will be reported in the BI 655066 safety database.

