2.3 BENEFIT - RISK ASSESSMENT

Results of the Phase I study with BI 655066 (study 1311.1) suggest that a single injection intravenously or subcutaneously (i.v. or s.c.) of BI 655066 is associated with substantial and durable improvements in the cutaneous manifestations of psoriasis. At doses of 0.25 mg/kg intravenously and above, all active dose groups showed improvement in mean PASI scores of at least 75% from baseline by week 12, which lasted at least until week 24. Similar improvements were observed in both of the active BI 655066 subcutaneous dose groups ([M14-0004](#)).

Patients rolling over in this OLE will have completed the single blind 1311.2 study where 75% of all patients will have received BI 655066 at different dose levels. Based on the preliminary data from study 1311.1 described in [Section 1.2](#), where good tolerability was

Proprietary confidential information.

© 2018 Boehringer Ingelheim International GmbH or one or more of its affiliated companies. All rights reserved.

This document may not - in full or in part - be passed on, reproduced, published or otherwise used without prior written permission.

shown, and no drug related serious adverse events (SAE), patients are likely to benefit from participation in this study.

Risks of participating in this study include risks related to the trial specific procedures such as blood sampling, subcutaneous injection of study medication. Blood sampling and subcutaneous injections can cause local bruising, inflammation, and pain.

As with any immune modulating agent, BI 655066 has the potential to impair immune function resulting in a risk of infection. This will be addressed by clinical monitoring for AEs during the treatment and follow up periods. Interferon gamma (IFN- γ) release assay to *M. tuberculosis* will be obtained at the initial roll-over visit, in order to exclude or discontinue documented untreated patients with active or latent tuberculosis infection (TB). All patients will be re-tested at the Extended end of treatment visit in order to assess long-term impact of BI 655066 on *M. tuberculosis* exposure. Patients having current signs or symptoms of infection or history of serious infection will not be included in the study.

The role of IL-23 in tumour immunity is not well established at this time, but an increased risk of cancer from an IL-23 antagonist, though considered small, cannot be excluded.

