4.2 CONCOMITANT THERAPY, RESTRICTIONS, AND RESCUE TREATMENT

4.2.1 Rescue medication, emergency procedures, and additional treatment(s)

In principle, any additional concomitant therapy considered necessary for the patient's welfare may be given at the discretion of the investigator. Stable doses of concomitant therapies for chronic conditions, for which neither the condition nor the treatment are judged to exclude the patient from participation (cf. [Section 3.3.3](#)), are permissible. However, all concomitant medications being taken by eligible patients must be carefully evaluated, and questions on the use of concomitant medications should be discussed with the BI clinical monitor.

In the event that a patient experiences an intolerable increase of psoriasis during the course of the trial, topical steroids of US class 6 (mild, such as desonide) or US class 7 (least potent, such as hydrocortisone) will be permitted for use limited to the face, axilla, and/or genitalia. Details of the drug used and the reason must be recorded in the electronic case report forms (eCRF). These topical medications should not be used within approximately 24 hours prior to visits requiring the PASI.

Investigational products are not allowed during the course of the trial.

In case of adverse events in need of treatment, symptomatic therapy according to the judgment of the investigator will be permitted. All concomitant and/or rescue therapies will be recorded on the appropriate pages of the eCRF.

There are no special emergency procedures to be followed.

Patients with a positive IGRA testing (Tb screening) at the roll-over visit should be followed-up according to local guidelines.

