5.2.3 Assessment of safety laboratory parameters

The laboratory parameters that will be determined are listed in [Tables 5.2.3: 1](#) and [5.2.3: 2](#) at the time points provided in [Flow Chart](#). The respective reference ranges will be provided in the ISF. The laboratory tests will be performed at a designated central laboratory, and if necessary by additional specialist laboratories.

Laboratory results of the patients will be available in real time to the respective investigator and to the clinical monitor of each country (central laboratory website), and selected

Proprietary confidential information.

© 2018 Boehringer Ingelheim International GmbH or one or more of its affiliated companies. All rights reserved.

This document may not - in full or in part - be passed on, reproduced, published or otherwise used without prior written permission.

abnormal laboratory alerts will be sent automatically to the sites and to the sponsor in real time. PK, PD and biomarker data will not be available to the investigators or local clinical monitors, but only to the Trial Team (sponsor) and to the DMC.

Clinically relevant laboratory values will be commented on in the eCRF. A clinically relevant value may be either in- or outside the reference range. Clinically relevant abnormal laboratory test results must be repeated using an unscheduled visit lab kit and must be repeated until normalisation or stabilisation or until an alternative explanation has been found. Clinically relevant abnormal laboratory values will be also graded for intensity by using RCTC Version 2.0 criteria.

The tests listed in Table 5.2.3: 1 constitute laboratory tests and hormones (assessed in female patients only) that will be done only at the initial roll-over visit and at Extended EOT or Extended EOS after approval of amendment # 5 and start of the rollover of patients to the M15-997 study from 01-May-2018, i.e. these tests are only required at EV1 for patients that are having EV1 as their first 1311.13 visit. The results will not be included into the report. Samples will be archived and run as clinically necessary.

Table 5.2.3: 1 Exclusionary Testing

Category	Test name
Tb screening	Interferon-gamma release assay (IGRA)
Serum pregnancy test (only female patients of childbearing potential)	Serum β -Human Chorionic Gonadotropin

Table 5.2.3: 2 Safety laboratory tests

Category	Test name

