6.2 DETAILS OF TRIAL PROCEDURES AT SELECTED VISITS

6.2.1 Screening and run-in period(s)

Patients in the 1311.2 trial that fulfil the criteria for roll over, either by response < PASI₅₀ between week 24 and week 44, or completing the entire preceding trial reaching week 48 according to protocol, will be asked to participate in this open label extension trial. Upon their agreement, they will immediately enter the treatment phase. Therefore, no screening or run-in procedures are defined in this protocol.

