- Inclusion criteria 3 (Negative serum β -Human Chorionic Gonadotropin (β -HCG))
Exclusion criteria 8 (Any clinically significant laboratory abnormalities)

Check consistency in medical history with the data obtained at visit 1 of the previous trial. All changes in medical history must be documented as adverse events and will be followed up as such during this trial.

Re-record ongoing adverse events/concomitant medications from the previous trial and record any adverse events/concomitant medications that may have started between the two trials, in the event that the 6 week time-window between trials was used.

All patients will be administered 90 mg BI 655066 s.c. at Extended visit 1.

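### Protocol 3.3.4.1 withdraws every patient with a positive roll-over IGRA, omitting the treated-tuberculosis exemption that exclusion criterion 4 grants

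*Protocol*

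**What the plan says.** Protocol 3.3.4.1 lists conditions under which a patient is to be withdrawn. One bullet covers clinically important acute or chronic infections, including "HIV and tuberculosis (including latent tuberculosis), or a positive interferon gamma release assay (IGRA) testing for tuberculosis", the assay being the roll-over one. The softer wording later in that section, under which a patient can be withdrawn after discussion, covers only eligibility violations and non-compliance.

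Exclusion criterion 4 in Protocol 3.3.3 is more lenient in two places. Its history bullet excludes "History of latent or active TB prior to screening, except for patients with documented completion of an adequate treatment regimen" at least 6 months before first study drug. Its IGRA bullet excludes a positive assay in which active disease has not been ruled out, then adds: "This does not apply to patients with history of latent tuberculosis with documented completion of an adequate treatment regimen", again at least 6 months beforehand. That bullet cross-refers to 3.3.4.1.

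Protocol 2.3 says the roll-over assay is taken "in order to exclude or discontinue documented untreated patients with active or latent tuberculosis infection (TB".

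On timing, 6.2.1 states: "Therefore, no screening or run-in procedures are defined in this protocol". Section 6.2.2.1 states: "All patients will be administered 90 mg BI 655066 s.c. at Extended visit 1". On handling, 4.2.1 says: "Patients with a positive IGRA testing (Tb screening) at the roll-over visit should be followed-up according to local guidelines". On whether a result will exist at all, 5.2.3 says: "Samples will be archived and run as clinically necessary".

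**The concern.** The withdrawal rule and the eligibility rule treat the same patient differently. Someone with adequately treated tuberculosis may remain IGRA-positive. The protocol deliberately admits that patient and doses the patient at Extended visit 1 (EV1), and then a positive roll-over result triggers mandatory withdrawal.

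The trial exists to collect long-term safety data and to give extended access, and a needless withdrawal costs both. The patient stays in the ITT and Safety Populations (SAP 5.1) but contributes no further doses. Any Week 48 PASI 90 value not yet collected is lost, and the observed-case rule in SAP 10.1 removes the patient from that denominator. The M15-997 offer also goes, because Protocol 3.1 and Flow Chart footnote 23 restrict it to patients who did not discontinue treatment early. A site that keeps the patient instead falls into the SAP 7.4 deviation category for subjects who developed withdrawal criteria and were not withdrawn.

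**Working it through.** The plan gives no figure to reproduce. The check applies each rule to three types of patient, all with a roll-over IGRA that is run and positive and with no sign of current active disease.

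| Patient | Exclusion 4 | Section 2.3 | 3.3.4.1, assay limb |
|---|---|---|---|
| Latent TB, adequately treated at least 6 months earlier, documented | Admitted by both the history and the IGRA bullets | Treated, so outside the group to be discontinued | Withdrawn |
| Active TB, adequately treated at least 6 months earlier, documented | Admitted by the history bullet; the IGRA bullet does not exclude once active disease is ruled out | Treated, so outside the group to be discontinued | Withdrawn |
| Untreated latent TB | Not the exempted group | To be excluded or discontinued | Withdrawn |

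Rows 1 and 2 conflict. Row 3 agrees with section 2.3.

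**Does another section supply the exemption?** Section 6.2.2.1 lists the criteria to re-assess once roll-over results arrive: inclusion 3 and exclusion 8. Exclusion 4 is not listed, so a late positive IGRA falls to 3.3.4.1. Section 4.2.1 asks for follow-up and is silent on staying in the trial. Neither repairs the gap.

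**When does the conflict bite?** The sample must be run and must be positive. Under the current Flow Chart (footnote 20) the EV1 assay applies only to patients whose first 1311.13 visit is EV1.

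**Week 48 value, if withdrawal is triggered by Extended visit 2.** SAP Table 1 targets Week 12 at Rx Day 85.
- Latest early end-of-treatment visit: 85 + 7 = Rx Day 92.
- Latest end-of-study visit: 92 + 84 + 7 = Rx Day 183.
- Week 48 window: [48×7 − 40, 48×7 + 43] = [296, 379].

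Neither visit reaches the window, so there is no Week 48 value.

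**Effect on a reported rate.** With n observed patients and rate p, dropping one responder moves the rate by (np − 1)/(n − 1) − p = −(1 − p)/(n − 1). Dropping one non-responder moves it by np/(n − 1) − p = p/(n − 1). Whatever p is, the shift is at most 1/(n − 1):
- n = 100, the planned total with no other losses (assumed): 1/99 = 1.0 percentage point.
- n = 25, one of four equal 1311.2 groups (assumed): 1/24 = 4.2 percentage points.

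**Close-out.** Assume nominal visit days and country approval by 01-May-2018. After that date the next visit is the last.
- To reach Week 48, the Week 36 visit (EV1 + 252 days) must fall by 01-May-2018, so EV1 must be on or before 22-Aug-2017.
- A patient with EV1 on the version date, 30-Jan-2018, has 91 days to close-out and would have no Week 48 value in any case.
- If EV1 is after 06-Feb-2018, EV1 + 84 days falls after 01-May-2018, so Extended visit 2 becomes the final visit and no later dose is lost.

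**The case against.** The strongest reply is that the intent is already clear. Section 2.3 names untreated patients for discontinuation as well as exclusion, the IGRA exclusion cross-refers to 3.3.4.1, and 4.2.1 points to local guidelines. On this view a site reading the whole protocol would keep the treated patient. The intent is indeed clear, but section 2.3 is benefit-risk background, while 3.3.4.1 is the operative rule and is mandatory. A site following the intent departs from the rule.

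A second reply is that strict withdrawal is a defensible caution with an immune-modulating drug, especially as a sample is run only for clinical need. It could be, had the protocol chosen it; section 2.3 states the opposite choice.

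Three limits stand in full. The trigger is narrow. This is the close-out version, and nothing in the documents shows new patients entering under it. Whether any patient with treated tuberculosis exists depends partly on 1311.2 entry criteria, which the documents do not give.

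A reader might also infer that the infection limb forces out everyone with past latent tuberculosis. The text does not support that: the limb is restricted to clinically important infections, and an investigator need not place treated past disease there. The positive-assay limb has no such qualifier, and the point rests on it alone.

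**Conclusion.** The inconsistency is real and confined to the assay limb of one bullet. Severity is minor. The number affected is unknown and may be zero. For one affected patient, a Week 48 rate moves by at most 1.0 point among 100 observed patients or 4.2 points in a group of 25; both denominators are assumptions. No hypothesis test, power figure or sample size depends on it.

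Three stronger readings are tempting and unsupported. First, a range of lost patient-years per patient: the loss can be zero near close-out, and any upper end would need the withdrawal bullet in superseded protocol versions, which cannot be read here. Second, that running the sample is enough to force withdrawal: the result must also be positive. Third, that 3.3.4.1 should exempt anyone in whom active disease has been ruled out: that would retain untreated latent tuberculosis, which section 2.3 says is to be discontinued.

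**What to change.** Add an exception to the assay limb of the 3.3.4.1 bullet, along these lines: *except a patient with past latent or active tuberculosis whose adequate treatment is documented as finished at least 6 months before first study drug, and who shows no sign of current active tuberculosis.*

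The exception should cover treated active as well as treated latent disease, because the history bullet of exclusion 4 admits both and section 2.3 targets only the untreated. Untreated patients with a positive assay are still withdrawn. The infection limb needs at most a matching clarification. Sections 2.3 and 4.2.1 and the SAP can stay as they are.

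The cost is one clause in one protocol bullet, with no change to any analysis.
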